1. RISKS TO SUBJECTS

a. Human subjects involvement and characteristics

Human subjects will be recruited from the MOVE Obesity Clinic at the West Los Angeles VA Medical Center within the VA Greater Los Angeles Healthcare System (GLAHS). They will be referred for study enrollment if they meet the inclusion criteria and do not meet any provisions of the exclusion criteria. The inclusion criteria include: men and women between 20 and 60 years of age, BMI 27 to 40 kg/m², non-smoker or stable smoking habits for at least 6 months prior to screening and agreement not to change such habits during the study. The exclusion criteria include weight change of > 3.0 kg in the month prior to screening, weight loss of > 10 kg in the 6 months prior to screening, calorie restriction diet (< 1500 kcal/day) for a period of 4 months or more in the 12 months prior to screening, use of any other investigational drug(s) within 8 weeks prior to screening, abnormal baseline laboratory parameters (serum creatinine > 1.6 mg/dl; ALT, AST, total bilirubin > 2.0 times the upper limit of normal; triglycerides > 500 mg/dl, total cholesterol > 350 mg/dl, TSH outside of normal range), consumption of more than 1 alcoholic beverage per day, pregnancy or intention to become pregnant. Following

informed consent, subjects will undergo randomization to either the normal protein diet or high protein diet groups. Both dietary interventions are consistent with clinical practice for management of obesity and do not pose any appreciable risk to the patient. Subjects will be asked to collect stool eleven times and to visit the VA clinical research unit seven times over 16 weeks.

b. Sources of material

Data and materials collected during the study will be used only according to the protocol approved by the VA Institutional Review Board (IRB). All information will be retained electronically behind the VA's electronic firewall except for regulatory documents and printed informed consent forms. All subjects will receive a unique research identifier number with the identities of the subjects retained only in a code key kept in a secure directory behind the firewall. Stool will be collected by techniques described in Aim 1 of the Research Plan. Demographic and medical data will be collected for all of the subjects according to the study protocol. Only the principal investigator (PI, [name]) and study coordinator will have access to confidential patient information.

c. Potential risks

1. Venipuncture - There may be some discomfort associated with obtaining peripheral blood. Rarely, venipuncture may result in the development of a hematoma. Venipuncture will be performed by a certified phlebotomist in the VA's Laboratory Medicine department.
2. Stool collection - This will be done privately by the study patients in their homes using materials provided to them by the study coordinator. There are no risks associated with self-stool collection.
3. Confidentiality - Aspects of the subjects' medical history will be obtained by the study personnel. All data will be retained within the VA's electronic firewall to ensure the greatest confidentiality.

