Study Protocol and Statistical Analysis Plan

Modulation of the Intestinal Microbiome by a High Protein Diet

NCT04812964

Document date: April 5, 2018

STUDY PROTOCOL: Modulation of the Intestinal Microbiome by a High Protein Diet

A. Design of randomized, controlled study comparing high and normal protein isocaloric calorie restriction diets for obesity.

Rationale and hypothesis: Based on my preclinical rodent model data, I hypothesize that a high protein diet will shift the composition of the microbiome of obese subjects, including increased *Akkermansia*, and that this will be associated with alterations of the metagenome (bacterial genes) and metabolome.

Study design: This hypothesis will be investigated in a randomized controlled study of the intestinal microbiome of an estimated 216 obese Veterans assigned 1:1 to isocaloric high protein (HPD) or normal protein (NPD) diets. The study will be advertised by posting flyers in the West Los Angeles VA Medical Center MOVE obesity clinic. MOVE physicians will provide interested patients with information about the study. Participants will undergo an initial screening visit in the clinical research unit after their MOVE appointment or on a later date. Once enrolled, participants will return to the clinical research unit for a baseline visit and follow-up visits on weeks 2, 4, 6, 8, 12, and 16 for dietary counseling, physical measurements, phlebotomy, and dietary questionnaires. The recruitment rate is estimated as 7 per month based on the recently completed study led by [name]. Patient recruitment and sample collection will be performed during the first 3 years of the study.

Inclusion criteria: Men and women between 20 and 75 years of age, BMI 27 to 40 kg/m², non-smoker or stable smoking habits for at least 6 months prior to screening and agreement not to change such habits during the study; subjects on non-obesity prescription medication may be included.

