Exclusion criteria: Weight change of > 3.0 kg in the month prior to screening, weight loss of > 10 kg in the 6 months prior to screening, calorie restriction diet (< 1500 kcal/day) for a period of 4 months or more in the 12 months prior to screening, use of any other investigational drug(s) within 8 weeks prior to screening, abnormal baseline laboratory parameters (serum creatinine > 1.6 mg/dl; ALT, AST, total bilirubin > 2.0 times the upper limit of normal; triglycerides > 500 mg/dl, total cholesterol > 350 mg/dl, TSH outside of normal range), consumption of more than 1 alcoholic beverage per day, pregnancy or intention to become pregnant.

Consent: Veterans will be consented during their screening visit. They must sign the VA GLAHS Institutional Review Board-approved written informed consent prior to the initiation of any study specific procedures or randomization.

Enrollment and randomization: Date of birth, sex, race, medical history, current medications, smoking and alcohol history will be obtained by the study coordinator during the screening visit. Eligible subjects will be assigned an enrollment number after signing the informed consent form then will be randomized to one of two diet groups.

Dietary intervention: Participants will be randomized to a HPD (30% protein, 40% carbohydrate, 30% fat) or a NPD (15% protein, 55% carbohydrate, 30% fat) with matched fatty acid profiles and fiber content. The diet will be implemented in two phases: an initial macronutrient standardized diet without calorie restriction for 2 weeks then the same macronutrient standardized diet with 1500 calorie restriction for 14 weeks. Subjects will receive dietary counseling during their baseline visit on their assigned macronutrient standardized diet. After 2 weeks of a macronutrient standardized diet, both groups will then receive further dietary counseling on how to restrict their intake to 1500 calories. Pea-based protein supplements will be provided to the HPD group to achieve the target of 30% calories from protein in the HPD group.

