Nutritional assessments: Participants will complete a three-day food record (3DFR) and the Food Frequency Questionnaire (FFQ) at every study visit to assess adherence to the prescribed macronutrient composition and calorie limit of the two dietary groups. The 3DFR consists of detailed documentation of food eaten on three days. FFQ is a self-administered, semi-quantitative tool that queries the average frequency of consumption over the prior one month of a list of food items. It will be modified to cover only 2 weeks on study visits at weeks 2 and 4. This study will use the Diet History Questionnaire supported by the National Cancer Institute and previously validated against other FFQs. The extensive nutrient composition database that supports the questionnaire allows estimations of the intake of macronutrients (e.g. fats), micronutrients (e.g. carotenoids), and specific food groups such as fruits, vegetables and grains.

B. Measurement of clinical response to the dietary interventions.

Primary and secondary endpoints: The primary clinical endpoint for response to dietary intervention will be weight loss. Secondary measures of clinical response will include change in fat mass, liver steatosis, lipids, and HgbA1c.

Clinical data collection: The following parameters will be obtained on each of 7 study visits: baseline, week 2, week 4, week 6, week 8, week 12, and week 16.

- 1) Physical examination: The study coordinator will measure height, weight, and waist/hip circumference.
- 2) Bioelectrical impedance analysis (BIA): Electrodes attached to a BIA device will be placed on the wrists and ankles. A brief electrical current will be passed to measure resistance and reactance, which can be used to calculate lean body mass and fat mass. One BIA device will be dedicated to this study.
- 3) Liver transient elastography (FibroScan): Hepatic steatosis and fibrosis will be evaluated by transient elastography, a non-invasive test that can be performed in 5 minutes using equipment that will be available down the hall from the clinical research unit where study visits will occur. Steatosis will be assessed by the CAP score and fibrosis by elastography with stiffness measured in kilopascals.

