- 4) Laboratory studies: Blood samples will be collected by venipuncture after 8-14 hours of fasting. Complete blood count, chemistry panel, lipids (total cholesterol, LDL, HDL, triglycerides), and hemoglobin A1c (HgbA1c) will be measured by the clinical laboratory at the West Los Angeles VA Medical Center.

Statistical analysis: Patient characteristics (physical measurements, lean body mass, laboratories, demographic traits) at baseline will be compared using a 2-sided t-test (for numerical variables) or chi-square test (for categorical variables) to evaluate the randomization. 3DFR and FFQ performed at each time point will be used to assess the predicted protein content of the patient's diet compared to baseline to evaluate the success of the dietary intervention. The significance of differences between the two groups in the primary and secondary outcome measures will be assessed using a 2-sided t-test.

C. Kinetic analysis of shifts in microbial composition in obese subjects (BMI 27-40) on a high protein diet compared to an isocaloric normal protein diet.

Fecal sampling: Participants will be provided with kits for home sampling. The subjects will urinate first then defecate into the Fisherbrand Commode Specimen Collection System. Subjects will use a spoon to transfer freshly defecated feces to a Para-Pak stool collection cup prefilled with 95% ethanol to fix the samples, allowing storage at room temperature for up to 2 weeks. Ethanol-fixed and fresh frozen samples give comparable metagenomics results to samples stored in preservatives such as RNALater while minimizing subjects' risk of exposure to toxic chemicals. The remaining feces will be frozen. This involves removing the cup from the

toilet hat, tightly closing the lid, and transferring the cup to a Ziploc bag for storage in the subject's freezer. Frozen samples will be delivered to the VA clinic during scheduled study visits using a Styrofoam box containing U-tek freezer packs designed to maintain a temperature of -20°C as was performed for a recent study. Reminder calls will be made 4 days before each study visit. Subjects who forget to bring in samples will be asked to either bring them in at the next visit or send them via overnight FedEx delivery. Samples will be stored at -80°C.

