2. ADEQUACY OF PROTECTION AGAINST RISKS

a. Recruitment and informed consent - Subjects will be recruited from patient populations being followed clinically at the VA's MOVE Obesity Clinic. Approved flyers will also be distributed. Inquiries by potential subjects will be initially directed to the study coordinator. Informed consent will be performed in a confidential and private manner. The PI and study coordinator will be able to answer any questions or concerns by the potential subject prior to obtaining informed consent. Although most patients being seen at the VA speak fluent English, in the event that a translator is needed one will be provided.

b. Protection against risks

1. Venipuncture - Collection of blood at baseline and during the course of the study will be conducted by trained and experienced phlebotomists in the VA Laboratory Medicine department. Every effort will be made to minimize the number of times that venipuncture is performed. Following disinfection of the skin surface, standard venipuncture techniques will be performed using a 22 or 25 gauge needle. A topical anesthetic can be made available should the subject have this preference. Following the blood draw, the area of the needle entry will be covered with gauze and pressure applied to minimize the development of a hematoma. A bandage will then be applied to the area. Should the patient experience a hematoma, the patient will be examined by a physician and standard clinical care will be employed to treat the hematoma.
2. Stool collection - Since there are no risks associated with collecting their own stool, patients will be instructed to perform the collection in the privacy of their home. The stool will be stored either in the subjects' freezers or at room temperature (after

fixation with 95% ethanol). Subjects will be warned not to consume the ethanol in the specimen cups. Samples will be returned in person to the study coordinator.

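### The plan does not exclude people on insulin or a sulfonylurea, adds calorie restriction and fasting visits, and states that the diets carry no appreciable risk, with no described drug review or hypoglycemia question

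*Combined protocol and SAP*

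**What the plan says.** **Who may enter.** Section A, Inclusion criteria, states that "subjects on non-obesity prescription medication may be included". The only drugs named in the Exclusion criteria are investigational ones. The laboratory limits cover creatinine, liver tests, triglycerides, cholesterol and TSH, with none for glucose or HgbA1c. D.1.a repeats these exclusions. Its inclusion list leaves out the medication sentence but adds no bar. Under Enrollment and randomization, "medical history, current medications, smoking and alcohol history will be obtained by the study coordinator during the screening visit". No later medication record is described.

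**What the study adds.** Both arms follow a standardized diet without a calorie limit for two weeks, then "the same macronutrient standardized diet with 1500 calorie restriction for 14 weeks". Section B, Clinical data collection, says: "The following parameters will be obtained on each of 7 study visits". Laboratory studies are among those parameters, and "Blood samples will be collected by venipuncture after 8-14 hours of fasting".

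**What it says about risk.** D.1.a states: "Both dietary interventions are consistent with clinical practice for management of obesity and do not pose any appreciable risk to the patient". D.1.c lists venipuncture, stool collection and confidentiality as the risks, and D.2.b gives protections for the same three.

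**What safeguards it has.** D.2.a says "Subjects will be recruited from patient populations being followed clinically", meaning at the MOVE clinic. In section A, MOVE physicians give interested patients the study information, and D.1.a speaks of referral for enrollment. Section E provides for general adverse event questioning, review by the PI, grading of association with the diets, reporting of all serious events, and reporting of a first unexpected event at any grade.

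**The concern.** Hypoglycemia is a foreseeable harm when someone eats less, or fasts, on an unchanged dose of insulin or a sulfonylurea. The study imposes both conditions on a schedule it sets itself, and nothing in the eligibility rules keeps these people out. The risk statement in D.1.a makes no exception for them.

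The risk section is detailed elsewhere: it covers hematoma care, a topical anesthetic and a warning about the ethanol in the specimen cups. A diet-drug interaction that can be serious belongs in the same place. At stake is participant safety and the accuracy of the risk statement. This point is not about the validity of the randomized comparison.

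**Working it through.** The plan gives no figure for this risk, so there is none to reproduce. The check sets the sections side by side and counts visits from the schedule.

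**Step 1: Can a person on insulin or a sulfonylurea enter?** The inclusion rule permits prescription drugs not given for obesity. The exclusions in section A and in D.1.a name no diabetes diagnosis, no glucose-lowering drug and no glucose or HgbA1c limit. Some exclusions (creatinine, liver tests, more than one drink per day) remove certain people more prone to hypoglycemia, but not users of these drugs as such. So entry is open to them.

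**Step 2: What exposure does the schedule create?**
- Visits with fasting blood draws: baseline and weeks 2, 4, 6, 8, 12 and 16 = 7.
- Length of restriction: 16 − 2 = 14 weeks, which agrees with the plan.
- Fasts before restriction takes effect: baseline and week 2 = 2.
- Fasts during restriction: 7 − 2 = 5 (weeks 4, 6, 8, 12, 16).
- Length of each fast: 8-14 hours.

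The first fast comes at baseline, two weeks before the calorie limit. A drug review timed only to the start of restriction would miss it.

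**Step 3: What does each described safeguard do?**

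| Safeguard | What it offers | What it leaves open |
|---|---|---|
| Medication list at screening | Identifies users of these drugs | No use of the list for safety is described, and no later record |
| MOVE physicians at entry | A clinician is generally involved | May not be the prescriber; no text says the fasts or the restriction date are passed on |
| Adverse event questioning and PI review (E.a, E.c) | The definition is broad enough to include hypoglycemia | General questions, asked after the event |
| Reporting to the IRB (E.c.5) | Covers serious events, and arguably a first mild episode | Acts after the event |
| Chemistry panel at each visit | Could show a low value on the day | No glucose review, threshold or action is described |

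No row describes a drug review before the first fast or before restriction, and no row asks specifically about hypoglycemia.

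**Step 4: How many people are exposed?** If a share p of the planned 216 take these drugs, the number is 216 × p. The document gives no p, so no headcount or event rate can be derived.

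**The case against.** The best case for the plan is that its safeguards are stronger than the risk section suggests. The adverse event definition in E.a is wide enough to take in a hypoglycemic episode. E.c.5 goes beyond serious events: it also requires a report of the first unexpected or previously unknown event, whatever its grade. Because the plan lists no diet risk, even a mild first episode could arguably go to the IRB. This is not certain, since the plan defines unexpected by reference to a product insert that is not part of the document. MOVE clinicians are also involved at entry, and the diets match ordinary obesity care, which is not disputed. All of this stands and narrows the gap. It does not close it, because reporting follows the event and no text links the study dates to whoever prescribes the drug.

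A reader might make four stronger inferences that the document does not support.
- That the plan knowingly enrolls people on glucose-lowering drugs. It never names such drugs; it only fails to exclude them.
- That hypoglycemia would go unrecorded. Section E would capture an episode that is recognized and mentioned.
- That the longer intervals between late visits measure the risk. They fall well into restriction, whereas an unchanged dose matters most at its start, when visits are two weeks apart. The reminder calls ("Reminder calls will be made 4 days before each study visit") belong to stool sampling and are not described as safety contacts.
- That the HgbA1c comparison is biased. Drug changes caused by a diet are part of the randomized effect.

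**Conclusion.** The point holds as a safety gap that should be fixed. For participants on insulin or a sulfonylurea, the unqualified risk statement in D.1.a is wrong. As written, the plan takes them through seven fasts, five of them under a 1500-calorie limit, with no described drug review beforehand and no specific question about hypoglycemia.

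The number of people affected is unknown and could be small. The conclusion rests on three assumptions: that some eligible patients take these drugs, which the document neither states nor rules out; that their doses are not otherwise adjusted around the study dates; and the general clinical premise that these drugs can cause hypoglycemia when intake falls.

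Consent pages are not in this copy, so what participants are told about fasting and medication is not judged. A reader should not conclude that they go unwarned, or that the diets are unsuitable for the wider study population.

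**What to change.** **Text.** Qualify the D.1.a sentence, for example: *The diets follow usual obesity care; in participants taking insulin or a sulfonylurea, calorie restriction and fasting visits can cause hypoglycemia.* Add this risk to D.1.c and its protections to D.2.b.

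**Before the first fast.** Flag these participants from the screening medication list. With the participant's permission, notify the prescriber of the fasting visits and of the date the 1500-calorie limit starts, preferably before baseline and no later than week 2. Do this in the same way in both arms and leave dosing to the prescriber. Permission is needed because D.1.b and D.2.b restrict confidential data to the PI and study coordinator, and a letter discloses participation.

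**During the study.** At the existing visits, ask flagged participants about hypoglycemia and about medication changes, and record episodes as adverse events.

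**Cost.** A short amendment, with consent wording if it is not already there; one permission and one letter per flagged participant; and slightly more questioning and adverse event recording. No new visits, tests or exclusions are needed. One downside is that some prescribers may cut doses pre-emptively, which could raise glucose; asking about medication changes would show this.

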2. ADEQUACY OF PROTECTION AGAINST RISKS

a. Recruitment and informed consent - Subjects will be recruited from patient populations being followed clinically at the VA's MOVE Obesity Clinic. Approved flyers will also be distributed. Inquiries by potential subjects will be initially directed to the study coordinator. Informed consent will be performed in a confidential and private manner. The PI and study coordinator will be able to answer any questions or concerns by the potential subject prior to obtaining informed consent. Although most patients being seen at the VA speak fluent English, in the event that a translator is needed one will be provided.

b. Protection against risks

1. Venipuncture - Collection of blood at baseline and during the course of the study will be conducted by trained and experienced phlebotomists in the VA Laboratory Medicine department. Every effort will be made to minimize the number of times that venipuncture is performed. Following disinfection of the skin surface, standard venipuncture techniques will be performed using a 22 or 25 gauge needle. A topical anesthetic can be made available should the subject have this preference. Following the blood draw, the area of the needle entry will be covered with gauze and pressure applied to minimize the development of a hematoma. A bandage will then be applied to the area. Should the patient experience a hematoma, the patient will be examined by a physician and standard clinical care will be employed to treat the hematoma.
2. Stool collection - Since there are no risks associated with collecting their own stool, patients will be instructed to perform the collection in the privacy of their home. The stool will be stored either in the subjects' freezers or at room temperature (after

fixation with 95% ethanol). Subjects will be warned not to consume the ethanol in the specimen cups. Samples will be returned in person to the study coordinator.

3. Confidentiality - All study related data will be managed in a confidential manner. The Department of Veterans Affairs has instituted a secure server system with 256-bit encryption that requires the use of a Personal Identity Verification (PIV) card to access the secure server or computer systems. In addition, our IT department will create space on the server for the entry and management of secure patient data. Only the PI and a study coordinator will have access to the secure data through their PIV cards. Each of these individuals have been certified by the VA's Research and Development Committee to access human data following the completion of mandatory training, including HIPAA training.

